## STUDY PROCEDURES

### *1. Procedures*

#### *Subjects*

Subjects will be 310 smokers who have been diagnosed with HIV/AIDS, meet study eligibility criteria, and provide written consent to participate in this between-subject trial.

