**Relapse Prevention Sessions (Weeks 3, 5, 7, and 9):** Participants will then receive 4 additional 20-minute in-person booster sessions at Weeks 3, 5, 7, and 9 which focus on either reinforcing success and reviewing the quit plan or reestablishing a quit date and restarting the cessation process. The counseling sessions are designed to enhance awareness of the harmful effects of smoking, assist the person in developing skills to quit and avoid relapse, and instruct the smoker on varenicline use. Lastly, all counseling sessions may be audiotaped and a random 15% of sessions assessed for protocol adherence. The counselor is blind to randomization.

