### **Other Smoking Measures (secondary)**

As per recommendations (Hughes et al., 2003), secondary smoking outcomes include: prolonged abstinence to Weeks 12 and 24 (relapse is 7 consecutive days of self-reported smoking, after a 2-week grace period), continuous abstinence at Weeks 12 and 24 (no smoking between the quit day and the follow-up; no smoking during weeks 9-12 as measured in previous varenicline trials with the general population of smokers; Gonzales et al., 2006), time to 7-day relapse (no grace period), smoking rate, and lapse (smoking episodes not lasting 7 days) and recovery (return to 24-hour abstinence) events (see [name] et al., 2010b). Abstinence and smoking rate outcome will also be available for Week 18.

**Cessation/Smoking Rate:** Daily smoking (presence and rate) will be assessed at each visit after Intake Session with the well validated timeline followback method (TLFB). These data can be used to assess the timing and rates of lapses (smoking episodes not lasting 7 days), recovery events (return to abstinence), and relapse events, as well as to monitor changes in smoking rates (i.e., # cigarettes/day). These data will also be used to compute and assess secondary measures of smoking cessation (e.g., continuous and prolonged abstinence).

**Carbon Monoxide (CO) Test:** Carbon monoxide will be measured at Intake and all subsequent visits to confirm smoking status.

**NicAlert™ Urine Dipstick (cotinine assessment):** Smoking status will be assessed with NicAlert™ urine dipsticks from Nymox Pharmaceutical Corporation

([http://www.nymox.com/products/nicalert/product\\_insert\\_for\\_urine.html](http://www.nymox.com/products/nicalert/product_insert_for_urine.html)). A midstream urine sample of approximately 25mL will be used to test for the presence of cotinine. Results will appear in one of seven category levels of usage. Level 0 indicates no detectable tobacco use; levels 1-2 indicate presence of cotinine, but as a non-user, and levels 3-6 indicate cotinine consistent with tobacco use. Participants with results in levels 3-6 will be considered smokers. The NicAlert™ urine cotinine assessment will be used to verify smoking status at Weeks 12, 18, and 24.

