**Aim 1: Compare 12-weeks of varenicline treatment and behavioral counseling to 12-weeks of placebo treatment and behavioral counseling for treating nicotine dependence among individuals with HIV/AIDS.** We will analyze quit rates using mixed effects logistic regression. The model will include a term for time-point and, possibly, a *small number of covariates as needed*. The hypothesized effect of treatment arm (placebo vs. varenicline) will be tested by including a dichotomous term for treatment arm; we will also test for an interaction between time-point and treatment. Outcomes of the logistic regression analyses will be characterized by odds ratios (e.g., odds of quitting smoking) and 95% confidence intervals. Although quit-rates at the end of 12 and 24 weeks will represent our primary outcome variables, similar logistic regression analyses will be performed for other measures of quit rates, including prolonged and continuous abstinence. In addition, many participants will fail to become completely abstinent, but may show a reduction in smoking. A secondary analysis will examine the effect of treatment arm on daily cigarette counts using mixed effects negative-binomial regression. Likewise, time to (recurrent) event models will be fitted using Cox regression, stratified by event sequence, as in [name] et al. (2010b), to assess lapse and recovery events over 24 weeks.

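### A lapse is defined by how long the smoking episode later lasts, and the plan does not say how the Cox model treats episodes that reach 7 days, so the lapse hazard ratio cannot be read as the effect on returning to smoking

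*Combined protocol and SAP*

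**What the plan says.** Other Smoking Measures (secondary) lists, among the secondary smoking outcomes, "lapse (smoking episodes not lasting 7 days) and recovery (return to 24-hour abstinence) events". The paragraph on cessation and smoking rate in the same section repeats the definition: "These data can be used to assess the timing and rates of lapses (smoking episodes not lasting 7 days". It names recovery and relapse events separately.

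Relapse is described in that section, for prolonged abstinence, as "relapse is 7 consecutive days of self-reported smoking, after a 2-week grace period". Episodes that reach 7 days also have a time-to-event outcome of their own, listed just before the lapse item: "time to 7-day relapse (no grace period), smoking rate, and lapse".

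Under Data Analysis, Aim 1, the method is that "time to (recurrent) event models will be fitted using Cox regression, stratified by event sequence", with the purpose "to assess lapse and recovery events over 24 weeks". For this method the text refers to the group's earlier trial of extended transdermal nicotine. It does not say whether an episode of 7 days or more is an event, a censoring, a competing event or continued time at risk, or when such a participant becomes at risk again.

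Re-entry matters because the later counseling sessions allow for "reestablishing a quit date and restarting the cessation process".

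**The concern.** A Cox model treats an event as something that happens at a point in time. Here, whether a return to smoking counts as a lapse is settled only by what follows: it counts if the episode stops before 7 days and not if it continues. The arm comparison then combines two quantities, how often participants start smoking again and how often an episode ends early. A drug that lowers the first lowers the lapse hazard. A drug that raises the second, also a benefit, raises the lapse hazard.

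The second effect is plausible on the plan's own rationale, since the Background says varenicline makes smoking less rewarding and eases withdrawal. At stake is the reading of one named secondary outcome: a lapse HR near or above 1 could be taken as no benefit, or as harm, when participants on varenicline return to smoking no more often and stop sooner.

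**Working it through.** **Plan's own figure.** There is none to reproduce: the plan gives no event count, HR or power for the lapse model.

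**Inputs from the documents.** Sample size: "Subjects will be 310 smokers who have been diagnosed with HIV/AIDS". The Risk/Benefit Assessment says half will receive varenicline, so 310 / 2 = 155 per arm. A lapse is an episode shorter than 7 days. Follow-up runs to Week 24 and the quit day is Week 1, so (24 − 1) × 7 = 161 days.

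**Assumptions, not in the documents.** Let λ be the daily hazard of starting to smoke from abstinence, and q the share of episodes that reach 7 days; P is placebo and V is varenicline.

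**Formula.** If long episodes are not counted as events and are censored at onset:

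- lapse hazard = λ × (1 − q)
- lapse HR = (λV / λP) × (1 − qV) / (1 − qP)

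**Direct evaluation.**

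| Onset HR | qP | qV | Lapse HR |
|---|---|---|---|
| 1.00 | 0.5 | 0.5 | 1.00 × 0.5/0.5 = 1.00 |
| 1.00 | 0.5 | 0.4 | 1.00 × 0.6/0.5 = 1.20 |
| 1.00 | 0.6 | 0.4 | 1.00 × 0.6/0.4 = 1.50 |
| 0.70 | 0.5 | 0.3 | 0.70 × 0.7/0.5 = 0.98 |
| 0.70 | 0.6 | 0.4 | 0.70 × 0.6/0.4 = 1.05 |

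**Range by speed of recovery.** With a constant daily chance r of stopping, q = (1 − r)^6. With equal onset hazards, for placebo and varenicline in that order:

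- r 0.05 and 0.10: q 0.735 and 0.531, HR 0.469/0.265 = 1.77
- r 0.10 and 0.20: q 0.531 and 0.262, HR 0.738/0.469 = 1.57
- r 0.10 and 0.15: q 0.531 and 0.377, HR 0.623/0.469 = 1.33
- r 0.20 and 0.30: q 0.262 and 0.118, HR 0.882/0.738 = 1.20
- r 0.30 and 0.40: q 0.118 and 0.047, HR 0.953/0.882 = 1.08
- equal r: HR 1.00

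The lapse HR exceeds 1 only if the true onset HR exceeds (1 − qP)/(1 − qV). For r 0.10 and 0.20 that is 0.469/0.738 = 0.64.

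**Simulation.** Because the plan is silent on long episodes, several codings were tried: 155 per arm, 161 days, everyone abstinent at the start, gap-time Cox stratified by event number, 40 runs per setting. Entries are HRs.

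| Onset per day, P / V | r, P / V | Every onset counts | Censor and stop | Censor and re-enter | Stay at risk |
|---|---|---|---|---|---|
| 0.030 / 0.030 | 0.10 / 0.10 | 1.01 | 0.97 | 1.00 | 0.99 |
| 0.030 / 0.030 | 0.10 / 0.15 | 1.01 | 1.32 | 1.33 | 1.43 |
| 0.030 / 0.030 | 0.10 / 0.20 | 1.01 | 1.60 | 1.60 | 1.83 |
| 0.030 / 0.030 | 0.20 / 0.30 | 1.00 | 1.19 | 1.18 | 1.26 |
| 0.030 / 0.024 | 0.10 / 0.20 | 0.80 | 1.25 | 1.25 | 1.46 |
| 0.030 / 0.015 | 0.10 / 0.20 | 0.51 | 0.77 | 0.77 | 0.96 |

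Both censoring codings follow the formula. Keeping participants at risk through a long episode moves the HR further up. Counting every onset recovers the true onset HR in each setting. In the third row, the three duration-based codings were significant for more lapses in 97% to 100% of runs. When onset is halved (last row), the benefit is understated but the sign does not reverse.

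**The case against.** The strongest reply is that the modelling rule is not written down. A reader might infer that the Cox model drops the longest episodes; the documents do not establish this. Aim 1 is silent on their coding, and the earlier trial it cites may have counted every onset. That stands: what the text shows is a duration-based definition joined to an unstated risk-set rule. It does not remove the point, because the definition is given twice and every coding tried that follows it produces the shift when episode lengths differ by arm.

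Second, long episodes are not lost to the trial. Time to 7-day relapse is a separate outcome, and a drug that shortens episodes should look better there. That also stands, and it limits the harm.

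Third, a reader might infer that the model would falsely report more lapses. Under the plan's own definition, short episodes really would be more frequent. The error lies in reading that HR as the effect on any return to smoking.

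Fourth, a reader might infer that the recovery analysis is compromised because episodes of 7 days or more are not lapses to recover from. The text does not support this: recovery is described as a return to abstinence and is not restricted to short episodes.

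Finally, the size depends on assumed values. With equal episode lengths there is no distortion, and with a large enough effect on onset there is no reversal.

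**Conclusion.** The concern holds in limited form. Taken literally, the lapse HR is the HR for returning to smoking multiplied by the ratio of the chances that an episode ends within 7 days. It therefore cannot be read as the effect on returning to smoking unless those chances are equal across arms. Over the assumed recovery rates, with no effect on onset, it runs from 1.00 (equal) to 1.77. Whether the sign reverses depends on how much varenicline shortens episodes relative to any reduction in onset. All rates are assumptions, and the algebra takes them as constant over time.

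One secondary outcome is affected, with no power statement attached. Nothing here bears on 7-day point prevalence abstinence at Weeks 12 and 24, or on time to 7-day relapse. The plan should still be changed, because the wording lets a benefit appear as harm and the repair is simple.

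**What to change.** In Other Smoking Measures (secondary) and in Data Analysis, Aim 1:

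- Define the lapse event as the first smoking day after at least 24 hours of abstinence, whatever the later length of the episode.
- Define recovery as the return to 24-hour abstinence from any such episode.
- Keep 7-day relapse as its own outcome.
- State the risk set: a participant is at risk of lapse only after reaching 24-hour abstinence, and re-enters at each recovery, including recovery after a 7-day relapse. Report by arm how many never enter it, because the lapse HR does not describe them.
- If short episodes are still reported, label that HR as specific to episodes under 7 days and show it beside the relapse HR.

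The cost is wording and recoding. The daily timeline follow-back records already hold what is needed, with no new data collection and no change to sample size.

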### **Quality of Life (QOL)**

The HIV/AIDS-Targeted Quality of Life scale (HAT-QoL; Holmes & Shea, 1998; 1999) measures overall functioning, which will be the primary measure of QOL for this study, but several subscales of QOL are also included such as life satisfaction, health worries, HIV mastery, financial worries, and disclosure worries which will be explored in Aim 2 analyses. This measure will be administered at each visit after the Intake Session.

### **Social Impact Assessments**

Several National Institute of Allergy and Infectious Diseases (NIAID)-sponsored groups have incorporated general assessments to measure the social impact of research participation in HIV vaccine trials (e.g. Social Impact Assessment used by the HIV Vaccine Trial Network HVTN; Allen, 2008). The Client Evaluation Form is a modified version of the well-validated Client Satisfaction Questionnaire (CSQ; Larsen et al., 1979; Sabourin et al., 1988) that contains 12 likert-scale type items assessing overall acceptability and satisfaction with the content and format of the ACASI-SHQ. The audio computer assisted self-administered interview social harm questionnaire (ACASI-SHQ) was designed to allow researchers to more easily identify and monitor social

harms experienced by substance abusers participating in HIV trials. It is hypothesized that the ACASI-SHQ will (1) reduce the likelihood of socially desirable responding by using the ACASI medium, (2) increase the likelihood of identifying social harms (construct validity) by including items with greater levels of specificity, and (3) increase the likelihood of its adoption by HIV researchers by utilizing a self-interview format. These assessments constitute a sub-study by co-collaborators [name] and [name] of the Treatment Research Institute.

## **2. Statistical Analysis**

### **Power**

Power is provided for the primary aims since the exploratory aim is hypothesis generating. Power calculations were all approximated as t- or z-tests (2-sided,  $\alpha = .05$ ), and conducted using PASS Software (Power and Sample Size, NCSS Software, Kaysville, UT).

Aim 1: The primary analysis is a comparison in week 12 and 24 cotinine-confirmed 7-day point prevalence quit rates between placebo and varenicline. For the week 12 comparison, we based our sample size selection on the expectation that quit rates in the placebo and varenicline arms would approximate those reported in past varenicline trials with the general population of smokers (i.e., placebo = 21.2%; varenicline = 50.3%; Gonzales et al., 2006). With a sample of 310, we have >90% power to detect a significant effect between our treatment arm. Notably, we have 80% to detect a difference in week 12 quit rates if the difference between treatment arms is as small as 15%, not 29% as found in Gonzales et al. (2006), since the effect for varenicline may be smaller in this sub-group of smokers. For the week 24 comparison, we based our sample size on the expectation that the quit rate in the placebo arm would be 14.5%, vs. 33.5% for varenicline (Gonzales et al., 2006). In this case, we have 85% power to detect a significant difference between treatment arms. However, we have 80% power to detect a difference between treatment arms if the treatment arm difference is only 15%, not the 19% reported in Gonzales et al. (2006), since the effect for varenicline may be smaller in this sub-group of smokers. Even though it may appear that we are over-powered for Aim 1, we require the proposed sample to conduct the non-inferiority analyses for Aim 2.

Aim 2: The analyses are a comparison in week 12 and 24 differences in QOL and severe side effects. For QOL, the overall scale mean among HIV/AIDS patients is 58.3 (SD = 24.5, Range 14-100; Holmes & Shea, 1998). We have 80% power to detect a mean difference of 7.8 at any time-point between the treatment arms with the proposed sample of 310. For side effects, the analyses will involve a test of non-inferiority since we cannot use standard statistical tests and conclude that a non-significant comparison shows that the drug is safe (i.e., "the absence of evidence is not evidence of absence"). In our past study with varenicline, 61% of participants on varenicline reported no severe side effects, vs. 76% of participants on placebo, a 15% difference (Patterson et al., 2009). With the present sample size, we will have 80% power to detect similar equivalence between treatment arms in terms of the frequency of severe side effects over the course of the 12-week treatment, given that side effects are actually non-significantly different across the treatment arms.

Aim 3: The analyses will assess changes in affect and cognitive function as mediators of treatment arm effects at week 12 and 24. These measures are continuous difference scores. Our sample of 310 is well above the minimum sample of 200 recommended for models of this size (Haduk, 1987; Boosma & Gabrielli, 1985). The mediation hypothesis will examine the proportion of treatment effect explained (Lin et al., 1997; Vittinghoff et al., 2009), and will test each mediation hypothesis with a z-score generated using the delta method. Our sample of 310 gives us 80% power to observe small effects in a 1-sample test ( $\delta=0.20$ ) when testing at  $\alpha=0.05$ . There are four proposed mediating pathways (2 measures of affect and cognition, respectively) between treatment and outcome, so our type-1 error will be corrected to 0.0125. Our sample of 310 gives us 80% power to detect small to medium effects ( $\delta=0.19$ ) for changes in the proposed mediators, which we have seen in previous trials (Patterson et al., 2009; [name] et al., 2010a).

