### 2. Accrual

For this trial, we project that we will screen ~1000 HIV/AIDS patients over 54 months (allowing six months to complete follow-up), 77% of whom will be current smokers ( $n = 770$ ). Additional data indicate that upwards of three-quarters of these patients will want to quit smoking and will want to use a medication in their quit attempt (Drach et al., 2010), yielding a sample of ~575 patients to recruit. Based on past varenicline trials ([name] et al., 2011; Patterson et al., 2009) and the present inclusion/exclusion criteria, we expect ~two-thirds of these patients to be eligible for the trial ( $n = \sim 345$ ). To be conservative, given the possible health problems evident in this population of smokers, we will project  $\leq 20\%$  of participants will withdraw from the trial and  $\geq 80\%$  of subjects will complete follow-ups. As is advised in smoking cessation trials (Hughes et al., 2003), intent-to-treat will be used for primary analyses, with missing outcome data coded as smokers.

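### Week-24 power is stated as 85%, but the plan's own inputs give about 98%; Aim 3's detectable effect of 0.20 at alpha 0.05 should be 0.16

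*Combined protocol and SAP*

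**What the plan says.** All the figures are in the combined protocol and SAP, section 2 (Statistical Analysis), under Power. That section says every calculation was approximated as a two-sided t- or z-test at alpha 0.05.

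- **Aim 1, week 24.** The assumed quit rates are 14.5% (placebo) and 33.5% (varenicline), with a sample of 310. The plan then says: "In this case, we have 85% power to detect a significant difference between treatment arms".
- **Aim 2, quality of life.** With an SD of 24.5: "We have 80% power to detect a mean difference of 7.8 at any time-point between the treatment arms".
- **Aim 3, before correction.** "Our sample of 310 gives us 80% power to observe small effects in a 1-sample test", with delta 0.20 at alpha 0.05.
- **Aim 3, after correction.** Alpha is reduced to 0.0125 for four mediating pathways. The next sentence reads "Our sample of 310 gives us 80% power to detect small to medium effects", with delta 0.19.

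Two other sections supply the remaining inputs. Section 6 (Risk/Benefit Assessment) says half the sample receives varenicline. Section 2 (Accrual) projects that at most 20% "of participants will withdraw from the trial" and makes intent-to-treat, with missing outcomes counted as smoking, the primary analysis.

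**The concern.** Week 24 is one of the two primary time-points, and every input to its power is printed beside the result. A 19-point difference from a low placebo rate with 155 per arm should give power well above 85%.

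In Aim 3 the two detectable effects run the wrong way. With the same N and the same power, a stricter alpha must raise the smallest detectable effect, yet the plan's value falls from 0.20 to 0.19.

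The stakes are limited. A reader cannot reproduce the power of a primary comparison from the plan, and the stated type II risk (15%) is about seven times the risk the inputs imply (2.2%). Both figures err on the low side, so the sample size is not threatened. The plan itself ties 310 to the non-inferiority analysis in Aim 2.

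**Working it through.** **Inputs.** N = 310 and two-sided alpha 0.05 (Power); 155 per arm (Risk/Benefit Assessment: half on varenicline); week-24 rates 0.145 and 0.335 (Power, Aim 1); loss up to 20% (Accrual); SD 24.5 (Power, Aim 2).

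**Step 1: which sample does the section use?** The quality-of-life figure settles this. The detectable difference is SD × (1.960 + 0.8416) × √(2/n):

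- n = 155: 24.5 × 2.8016 × √(2/155) = 7.80, which matches the stated 7.8.
- n = 124 (20% loss): 24.5 × 2.8016 × √(2/124) = 8.72, which does not.

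So this figure uses all 310 patients with no allowance for loss. The week-12 claim of more than 90% for 21.2% against 50.3% also holds at 155 per arm (computed above 99.9%).

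**Step 2: week-24 power.** For the pooled z-test, power = Φ{[d − 1.960 × √(2p̄(1 − p̄)/n)] / √([p₁(1 − p₁) + p₂(1 − p₂)]/n)}, with d = 0.19 and p̄ = 0.24.

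- Standard error under the null: √(2 × 0.24 × 0.76/155) = 0.04851.
- Standard error under the alternative: √((0.1240 + 0.2228)/155) = 0.04730.
- Power: Φ[(0.19 − 1.960 × 0.04851)/0.04730] = Φ(2.007) = **97.8%**.

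The choice of test does not explain the gap: unpooled z 98.0%, arcsine 97.9%, Fisher exact 97.1%, continuity-corrected 96.9%.

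**Step 3: could loss explain 85%?**

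| Basis | Rates | n per arm | Power | With continuity correction |
|---|---|---|---|---|
| No loss | 14.5% vs 33.5% | 155 | 97.8% | 96.9% |
| 20% removed | 14.5% vs 33.5% | 124 | 94.3% | 92.4% |
| 20% counted as smoking | 11.6% vs 26.8% | 155 | 92.9% | 90.6% |

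The third row multiplies both rates by 0.8. It assumes equal loss in the arms and cited rates that do not already count missing as smoking. No row reaches 85%. Solving for n, 85% needs about 90 per arm (85.3%), or 100 with continuity correction. A value near 85% does appear if 124 per arm is combined with alpha 0.0125 (84.9%), but the plan uses that alpha only for the Aim 3 pathways.

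**Step 4: Aim 3.** For a one-sample test at 80% power, δ = (z₁₋α/₂ + 0.8416)/√N, with √310 = 17.607:

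- alpha 0.05: (1.960 + 0.8416)/17.607 = **0.159** (plan: 0.20).
- alpha 0.0125: (2.498 + 0.8416)/17.607 = **0.190** (plan: 0.19, reproduced).

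The t-distribution gives 0.160 and 0.191. In the other direction, the power for δ = 0.20 at alpha 0.05 is Φ(0.20 × 17.607 − 1.960) = Φ(1.561) = 94.1%. The N needed for 80% is (2.8016/0.20)² = 196.2, so 197 patients. The value 0.20 therefore fits a sample of about 200 (0.198). The same paragraph names 200 as a recommended minimum, but nothing shows that this is where the figure came from.

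**Step 5: the neighbouring 15-point statements.** The plan claims 80% power for a 15-point difference at each time-point without repeating a placebo rate. At the stated placebo rates and 155 per arm, power is 83% at week 12 (21.2% vs 36.2%) and 89% at week 24 (14.5% vs 29.5%). Both can be read as at least 80%, so neither is shown to be wrong.

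**The case against.** The best defence is that these are conservative floors. The computed week-24 power exceeds 85% in every row of the table (lowest 90.6%), and an effect of 0.20 does have at least 80% power. If the 15-point statements may be read as lower bounds, why not these? In addition, 0.20 may simply be the conventional label for a small effect, and the 0.19 sentence names neither its alpha nor its test. Finally, the figures are a priori and change no decision: the current text is Version 19 of February 2018, while the plan projected completion in December 2016.

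Some of this stands. The impact is low, and that 0.19 is a one-sample value at 0.0125 is inferred from its position and the numerical match.

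The rest does not. The week-24 sentence states a value, while the same paragraph marks its week-12 figure as a bound with a greater-than sign. The 15-point statements lack a placebo rate, whereas the week-24 sentence gives all its inputs and still misses by about 13 points. For Aim 3, the sentence attaches 80% power to 0.20, and the computed power is 94.1%. Reading 0.19 another way does not help: if it also belonged to alpha 0.05, two different effects would have the same power at the same N and alpha. A two-sample test would give 0.38 at alpha 0.0125 or 0.32 at 0.05, so 0.19 fits neither.

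**Conclusion.** The concern holds. Week-24 power for 14.5% against 33.5% is 97.8%, not 85%, assuming equal arms, all 310 analysed and the stated two-sided 0.05 z-test. Under 20% loss it is 93% to 94% (91% to 92% with continuity correction), assuming that 310 is the number randomized. The Protocol Abstract says so, although Target Population says 310 will complete the study. In Aim 3 the detectable effect at alpha 0.05 is 0.16 rather than 0.20, and the 0.19 at alpha 0.0125 is correct.

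These are reporting errors in stated power figures. Both understate power. The sample size, alpha levels and planned analyses are unaffected.

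**What to change.** In Power, Aim 1, replace 85% with about 98% and state the basis: 155 per arm, no loss. If the authors meant to include 20% loss, they should instead give about 93% to 94%, after confirming that 310 is the number randomized and how the cited rates treat missing outcomes.

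In Power, Aim 3, replace 0.20 with 0.16, and label 0.19 as the one-sample detectable effect at alpha 0.0125.

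Optionally, give the placebo rate and loss basis behind the two 15-point statements so that they can be checked.

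The cost is a few words of text. There is no change to the sample size, conduct or analysis.
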